The following are power estimates based on 10000 simulations under the above conditions for various feasible sample sizes. We also obtained power estimates for the scenario involving a 2% infection rate in the control group (OD).

Sample size/arm	Reference Proportion	Power ($\Delta=0.03$)	Power ($\Delta=0.04$)	Power ($\Delta=0.05$)	Power ($\Delta=0.06$)
70	0.01	0.5091	0.6766	0.8536	0.866
80	0.01	0.5164	0.8107	0.8382	0.9434
90	0.01	0.4865	0.786	0.8734	0.9489
100	0.01	0.7416	0.7878	0.9254	0.9616
110	0.01	0.6994	0.8383	0.9245	0.976
120	0.01	0.6926	0.894	0.9437	0.9763
130	0.01	0.714	0.8738	0.9621	0.981
140	0.01	0.6907	0.8783	0.9624	0.99
150	0.01	0.7606	0.9111	0.9748	0.9928
160	0.01	0.8221	0.9394	0.9816	0.997
170	0.01	0.795	0.9427	0.9842	0.998
180	0.01	0.821	0.9339	0.9876	0.9984
190	0.01	0.8147	0.9573	0.9936	0.9987
200	0.01	0.848	0.9629	0.9928	0.9987
210	0.01	0.8503	0.9669	0.9941	0.9995
220	0.01	0.8675	0.9743	0.9961	0.9992
130	0.02	0.4748	0.6378	0.8123	0.9066
140	0.02	0.4906	0.6922	0.8385	0.9288
150	0.02	0.5051	0.7048	0.8785	0.9466
160	0.02	0.5642	0.7452	0.8678	0.9593

170	0.02	0.5458	0.7621	0.8958	0.9679
180	0.02	0.5651	0.7737	0.9165	0.9682
190	0.02	0.5864	0.8088	0.9317	0.9733
200	0.02	0.5865	0.8005	0.9275	0.9807
210	0.02	0.6349	0.8346	0.943	0.9833
220	0.02	0.61	0.842	0.9504	0.9868

For outcome of healing time (**Specific Aim 2**), most fractures have a healing time of 6 weeks with an estimated standard deviation of 1 week. We will again try to show ED management is not inferior with respect to healing time when compared to OR management, assuming a margin of non-inferiority of one week ($\Delta=1$). Assuming a one-sided 0.025 level of significance and power ($1-\beta$) equal to 0.90, the number of subjects required per treatment group can be calculated as follows:

$$H_0: \mu_C - \mu_T \geq \Delta \quad \text{vs.} \quad H_1: \mu_C - \mu_T < \Delta$$

$$N = \frac{2(Z_{\alpha} + Z_{1-\beta})^2 \sigma^2}{\Delta^2}$$

$$N = \frac{2(1.96 + 1.282)^2 1^2}{1^2} \qquad N = 21$$

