Our results suggest that a **sample size of 150 per group (300 total)** would provide 91% power to detect non-inferiority of emergency room management when compared to operating room treatment in the type one open fractures under the assumptions outlined above. We have accepted a 5% infection rate (4% shift from the hypothesized reference rate). If the baseline infection rate is 2%, this study would be adequately powered (87%) to show non-inferiority for a margin of 5% (7% infection rate in the ED arm). As the calculation above illustrates, the study is also well powered to demonstrate non-inferiority with respect to healing time.

Site estimates:

The following sites have provided the initial estimates as to how many patients they feel could be enrolled in a given year: Lurie Children’s = 2/year, Vancouver Children’s Hospital 5/y, Riley Children’s= 2/y, University of Mississippi Medical Center = 9/y, Mary Bridge Children’s Hospital= 12/y, Yale-New Haven Children’s Hospital= 4/y, Carrie Tingley Children’s Hospital= 20/y, Phoenix Children’s Hospital= 20/y, Nationwide Children’s Hospital= 20y, IWK Health Centre, Halifax=4/y, Denver Children’s Hospital=12/y. Texas Children’s Hospital= 12/y, Morristown Medical Center = 2/y, New York University Medical Center = 4/y. Approximate Total= 128/y.

Subject Recruitment:

The number of subjects needed for this trial is large. To date, the pilot study has had an excellent recruitment (80% see below) rate, so we expect similar rates at participating centers.

Currently, with the 14 sites who have agreed to participate thus far, the expected recruitment is 128 patients per year. We plan to add 4-6 more sites during the Planning Grant Period which would expand the projected total recruitment to 160 patients per year. Therefore, when the study is at full capacity, we conservatively anticipate recruiting 120 patients per year (assuming 75% recruitment rate) over the 3 year grant period, for a total of 360 patients, which surpasses the calculated 300 patients needed for adequate statistical power. We are accepting and powering for a 5% infection rate in the ED arm. If we were to accept a 6% infection rate (i.e., a 5% margin of non-inferiority) then we would require only 190 patients. For a 7% infection rate ($\Delta=0.06$), we will need 150 patients. If recruitment is lower than expected, we could accept a larger

margin of non-inferiority given the large range of type I open fracture rate (0-10%) in the literature.

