We will use an independent two-sample confidence interval for binomial proportions comparing infection rates between the two treatment arms. If the upper limit of a two-sided, 95% confidence interval is less than the margin of non-inferiority, we will have evidence that ED management is not inferior to OR management. Similarly, an independent two-sample confidence for difference in mean healing time will be constructed and used in the same manner to determine evidence of non-inferiority. Both large sample, normal approximation methods and exact methods will be explored. Descriptive data will be used to relay anesthesia complications, additional procedures and significant infections. Primary analysis will be based on the "as treated" principle, and an intent-to-treat analysis will also be conducted. We expect almost no cross-over in the initial 24 hours after injury. We will also use Kaplan-Meier estimation to create curves comparing cumulative incidence of infection as well as time to healing for the duration of study follow-up.

Data Security:

Research Electronic Data Capture (REDCap)

REDCap is a secure application used for managing online databases for collecting research data. The software allows data to be stored over a secure web connection with authentication and data logging features. The database creates a log of all activity including information such as the date, time and user who performed the action. The database is password protected and only approved users are able to access projects through REDCap. Data for all sites involved in this multi-center project will be stored in this electronic database. PIs and research coordinators from each site

will be assigned Northwestern University Affiliate NetIDs which will give them access to REDCap through Northwestern University Clinical and Translational Sciences Institute (NUCATS). Once these NetIDs are granted, the research coordinator at Lurie Children's will then add these individuals to the REDCap project.

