The main ethical issue associated with this research would be if there is an increased infection rate with children who are randomized to the non-operative arm. These children may require longer term antibiotics or additional surgery. However, if a single surgery is ultimately necessary, the patient may only have lost minor healing time since a surgery was saved initially. Due to the fact that there are now three case series reporting children treated nonoperatively for minor open fracture, multiple centers are using it as their standard treatment practice. While these retrospective studies do not demonstrate an increased infection rate, these case series were all underpowered to show a significant difference. In our survey to POSNA membership, 31% of respondents chose emergency room treatment while 69% chose an operative strategy in the treatment of type I open forearm fracture. Therefore, equipoise exists for this question. The main benefit of this study will be to future children with open fractures. The children in the study will benefit if they were randomized to the ED group and the data shows no signs of infection and a normal healing time because they will have avoided a trip to the operating room.

Risks to Participants:

Patients with Type I open fractures are generally at minimal risk of problems if treated appropriately. The fracture should be treated within 24 hours of the injury to avoid infection. Infections may be caused by bacteria that contaminate the wound at the time of injury. Infections are unusual with this injury and can occur whether the child is taken to surgery. Infection may result in slow healing of the fracture and chronic bone infection. All children with fractures may also experience injury to the nerves or arteries or excessive swelling which can cause injury to muscle tissue. Risks of anesthesia in the Emergency Department or operating room may include breathing problems but are very rare in a previously healthy person. Participants who undergo surgery will be told of the risks related to anesthesia and surgery at that time and will sign a separate, treatment consent for the surgery and anesthesia. Risks of fracture treatment may include alignment problems or poor bone healing. Unknown risks may be involved with this research study.

Benefits:

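### Aim 2 is decided on a difference in mean healing time with no rule for a child who has no observed union, so an excess of non-union in the ED arm may never enter the decision

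*Combined protocol and SAP*

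**What the plan says.** Section A defines the Aim 2 response as the time until the fracture has healed clinically and radiographically. Under Ascertainment of response variables, union needs callus on three of four sides of the bone and no tenderness. Follow up visit description and schedule lists visits up to about 24 weeks.

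The decision rule is in the Data Analysis section that follows Data management: "an independent two-sample confidence for difference in mean healing time will be constructed and used in the same manner to determine evidence of non-inferiority". The manner meant is the infection rule, in which the upper limit of a two-sided 95% interval must lie below the margin. Sample size assumptions and estimates gives the design figures: "most fractures have a healing time of 6 weeks with an estimated standard deviation of 1 week", and "assuming a margin of non-inferiority of one week".

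The same Data Analysis section also plans "Kaplan-Meier estimation to create curves comparing cumulative incidence of infection as well as time to healing for the duration of study follow-up". Final analysis mentions Kaplan-Meier curves again. Neither place attaches an estimate, a margin or a test to them. The primary analysis is as-treated, with an intent-to-treat analysis alongside.

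No section says what healing time is given to a child whose fracture has not united at the last visit, or who is lost before union. There is no censoring rule for the mean, no assigned value, no imputation and no allowance for loss.

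**The concern.** A mean needs one number per child, and a child without an observed union has none. The normal-approximation and exact methods that the plan will explore both need that number, and choosing as-treated or intent-to-treat settles the arm, not the time. Someone will have to choose at analysis, possibly after seeing the data, and the easiest choice is to leave these children out.

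That choice is not neutral in a non-inferiority comparison. Risks to Participants says: "Infection may result in slow healing of the fracture and chronic bone infection". A missing union date may therefore be related to the harm the trial is looking for. If more ED children fail to unite and they are left out, the arms look more alike than they are, and the error favours ED management.

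The timeline adds a smaller source of missing dates. Accrual ends in August 2016 and follow-up in December 2016, described as six months. Even to the end of December that is about 17 to 22 weeks, so some late enrollees may not reach a 24-week visit.

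**Working it through.** **Inputs from the plan.** Mean 6 weeks, SD 1 week, margin 1 week, one-sided 0.025, power 0.90 (Sample size assumptions and estimates); "sample size of 150 per group (300 total", that is, 300 in total; last visit at about 24 weeks. I take the difference as ED minus OR, with longer healing worse.

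**Assumptions, not from the plan.** Children who unite have Normal(6, 1) times in both arms. Un-united children are counted to 24 weeks. Unless stated otherwise, none are in the OR arm.

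**The plan's own figure.** N = 2 × (1.96 + 1.282)² × 1² / 1² = 21.02. The plan reports 21 (22 if rounded up), so it reproduces. Power at 150 per arm is above 0.999. Precision is not a problem while every child has a healing time.

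**Effect of one child.** (24 − 6)/150 = 0.12 week added to the ED mean.

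**Five un-united in ED, none in OR**
- Left out (145 versus 150): expected difference 0, SE = √(1/145 + 1/150) = 0.116, upper limit 1.96 × 0.116 = 0.23 week. Non-inferiority was shown in 100% of 20,000 simulated trials.
- Counted to 24 weeks: difference 5 × 0.12 = 0.60. With f = 5/150, the ED variance is (1 − f) × 1 + f(1 − f) × 18² = 0.967 + 0.0322 × 324 = 11.4. SE = √((11.4 + 1)/150) = 0.288. Upper limit = 0.60 + 1.96 × 0.288 = 1.16 weeks. Non-inferiority was shown in 7% of simulated trials.

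**Nine un-united in ED, none in OR.** The difference first passes the margin at nine, because 1/0.12 = 8.3.
- Left out (141 versus 150): upper limit 1.96 × √(1/141 + 1/150) = 0.23 week, so non-inferior.
- Counted to 24 weeks: difference 9 × 0.12 = 1.08 weeks, already beyond the margin. With f = 0.06, variance = 0.94 + 0.0564 × 324 = 19.2, SE = √(20.2/150) = 0.367, upper limit 1.08 + 1.96 × 0.367 = 1.80 weeks.

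**Sensitivity to the assumptions (upper limits and reversal numbers)**

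| Time assigned to un-united ED children | Upper limit with five | Smallest number taking the upper limit to 1 week |
|---|---|---|
| 12 weeks | 0.48 | 16 |
| 17 weeks | 0.76 | 8 |
| 24 weeks | 1.16 | 4 by t (1.001), 5 by z |

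If OR children are un-united too, also counted to 24 weeks, the ED number needed is 5 (with 1 or 2 in OR), 6 (with 3) or 7 (with 5). At 75 per arm, the size at which Subject Recruitment allows halting to be considered (150 patients in total), two ED children at 24 weeks are enough.

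**The case against.** The other side has several good points.

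- **Exclusion is not stated.** A reader might infer that the plan drops every child without a union date. The text is silent. Assigning the last-visit time would fit it equally well. What can be shown is that the handling is undefined and that omission is the easiest course.
- **Delayed union does not vanish.** A child who unites by the 12- or 24-week visit has a date and raises the mean. Only children un-united at the last visit, or lost earlier, are affected.
- **Five children do not produce a false conclusion.** It is tempting to say that five reverse a wrong result. But 0.60 week is inside the margin. The fall from 100% to 7% comes from the SE rising from 0.116 to 0.288, which is lost precision. A true difference beyond the margin takes about nine against none.
- **Nothing makes such numbers likely.** No non-union rate is given, and D. Previous Work reports no delayed healing in the twelve pilot patients. At the 5% ED infection rate the design accepts, 150 × 0.05 = 7.5 children would be infected, so infection alone would not supply nine.
- **The children stay visible.** Kaplan-Meier curves are planned, and a blinded surgeon reviews all radiographs. An excess of non-union could be seen.

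All of this stands, and it narrows the point. It does not supply a value for a child without union, nor give the curves any part in the decision.

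**Conclusion.** The point holds in a limited form. The statistic that decides Aim 2 cannot take in a child without an observed union, and the plan does not say what happens to that child. If such children are left out, an excess of non-union in the ED arm has no influence on the decision: the expected upper limit stays at about 0.23 week whether five or nine are missing.

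Counting them to 24 weeks at 150 per arm, five against none means that non-inferiority is no longer shown, and nine against none means that the margin is truly exceeded. Both figures rest on equal healing among the other children, no un-united OR children and the 24-week value; they weaken quickly with shorter assigned times. Since the documents give no non-union rate, this shows how the rule can fail, not that it will. It is worth changing because the change is small and the possible error runs in the direction the trial should guard against.

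**What to change.** Base the Aim 2 decision on the ED minus OR difference in restricted mean time to union up to 24 weeks, taken from the Kaplan-Meier curves already planned, in both analysis sets the plan names (as-treated and intent-to-treat). Count children un-united at 24 weeks to 24 weeks, and censor children lost earlier at their last radiograph. Compare the upper 95% limit with the one-week margin, and have the investigators confirm that one week is the margin they intend for a restricted mean. Report by arm the number un-united at 24 weeks and the number lost before union.

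This takes a few sentences in the analysis section and a little programming, with no new data. The price is a wider interval when some children are un-united: an SE of about 0.29 against 0.12 in the five-child example. Two limits remain. Censoring assumes that loss is unrelated to healing, which is why the counts by arm matter. A small excess can also still pass: three against none gives an upper limit of about 0.82 week.

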Of the thirteen patients who agreed to participate, six were randomized to emergency room treatment and seven were randomized to operating room treatment. One of the patients, randomized to operating room treatment fracture was NOT found to have an open fracture and

will be eliminated from final formal assessment beyond intent to treat analysis. Another patient who was randomized to the operating room chose not to undergo surgery and instead received ED treatment only. None of the twelve patients' fractures, enrolled in the study, were complicated by infection or delayed healing. There have been no differences in anesthesia/sedation related complications.

E. Methods:

Clinical Trial Portion

Design of the study: A prospective, randomized unblinded non-inferiority clinical trial of children with Type I open fractures to evaluate whether emergency room management and close follow up will not be inferior to formal operative irrigation and debridement in terms of infection rates and bone healing times. The baseline rate of infection with open fractures, treated operatively, is noted to be 0-10% in the literature. We will choose a baseline infection rate of 1%.

Study population:

Inclusion Criteria - Patients will be included if their age is between 3 and 14 years, if the fracture is amenable to treatment by closed reduction, a low energy injury (falls from less than 10 feet, bicycle accidents), wounds less than 1 cm in length and the bone not visualized through the skin.

Exclusion Criteria - Patients will be excluded if they do not meet inclusion criteria, if the fracture would typically require operative reduction and fixation, if their mechanism was high energy (struck by vehicle, motor vehicle accidents, fall from height greater than 10 feet), if there is gross contamination of the wound, or if the open injury involved the hands or feet (the current standard of care to treat open injuries involving hands or feet is only emergency room management).

Study Procedures:

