Baseline assessment will include the child's age, mechanism of injury, bone fractured, wound side and location, state of skin injury, whether gross contamination is present, neurovascular status, comorbid conditions.

Additionally, if patients do not wish to be randomized to a treatment arm, they will still be presented with an option for study enrollment. They may take part in a prospective chart review in which the same data will be collected as those patients who were randomized. The data collected at both the baseline and follow-up will match the data collected from patients who randomized to a treatment arm. Patients will consult with their physician regarding treatment for their injury and decide which treatment method they prefer. They will then be consented by the study coordinator or an investigator who will describe the study and the data that will be gathered from their medical charts.

Intervention allocation:

The randomization assignment will be completed and accessible only by the study coordinator. The coordinator will have the assignments in numbered, sealed, radio opaque envelopes in sequential order by the study site. The envelopes will be made by an independent study assistant and determined by block allocation with a 1:1 ratio of operative room vs. emergency room management with permuted, mixed blocks of 4 and 6 created randomly. Randomization will be stratified by each center but by no other factors. The order of these permuted blocks will be determined by random number chart.

Experimental and Control Interventions:

Children will be randomized into two treatment arms – formal operative management (OR) and emergency department (ED) management. Children randomized to the OR arm will be taken to the OR within 24 hours for irrigation and debridement and appropriate bone management. Patients who randomize to non-operative treatment will only be given conscious sedation in the emergency department where the bone will be reduced and casted and the wound will be washed out with one liter of normal saline. All patients will be admitted for 24 hours of intravenous antibiotics post treatment and then sent home with 7 days of oral antibiotics.

Follow up visit description and schedule:

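### Healing time is compared without adjustment for age, bone or centre; a pre-specified adjusted model would be a cheap but optional gain in precision

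*Combined protocol and SAP*

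**What the plan says.** The Data Analysis section (after Data management) compares the arms on infection with a two-sample interval for proportions. For healing it says "an independent two-sample confidence for difference in mean healing time will be constructed and used in the same manner". Kaplan-Meier curves are added. No section names a covariate or a centre term for either comparison. The as-treated analysis is primary, an intent-to-treat analysis is also planned, and almost no crossover is expected in the first 24 hours.

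The covariates will be available. Under Study Procedures, "Baseline assessment will include the child's age, mechanism of injury, bone fractured" among other items, and Data management lists age and bone again. The population is broad: "Patients will be included if their age is between 3 and 14 years", and only hand and foot injuries are excluded by site. Intervention allocation stratifies by centre alone.

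For sample size the plan states that "most fractures have a healing time of 6 weeks with an estimated standard deviation of 1 week", "assuming a margin of non-inferiority of one week". It arrives at 21 per group, against 150 per group set by the infection endpoint.

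**The concern.** The Significance section says that open fractures differ by bone and skeletal maturity, and that children's thick periosteum may shorten healing. Age and bone are therefore plausible predictors of healing time, though the documents support this only in words. Leaving recorded predictors and the stratification factor out of the analysis gives an interval wider than it need be.

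Two features of this plan make the omission more than a matter of style.

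- **As-treated primary analysis.** Children who switch arm are not compared as randomised, so baseline differences between those who switch and those who do not can enter the estimate.
- **Visit schedule.** Healing is read at visits at about 1, 2, 4, 6, 12 and 24 weeks. The recorded times may be far more spread out than the planned SD suggests.

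At stake is the precision of the healing-time conclusion. The infection endpoint is not affected.

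**Working it through.** **Inputs from the documents.** Mean 6 weeks, SD 1 week, margin 1 week, one-sided 0.025, power 0.90 (Sample size assumptions and estimates); 150 per arm; a possible stop at 150 patients in total, that is 75 per arm (after Subject Recruitment); the visit schedule above. **Assumed:** the share of variance explained by the covariates, R², from 0.1 to 0.4.

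**1. The plan's own figure.** N = 2(1.96 + 1.282)² × 1²/1² = 21.02. The stated 21 reproduces (22 if rounded up).

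**2. Unadjusted interval at the planned size.** SE = 1 × √(2/150) = 0.1155 week. Half-width = 1.96 × 0.1155 = 0.226 week. Power = Φ(1/0.1155 − 1.96) = Φ(6.70), above 99.9%. At 75 per arm the half-width is 0.320 week and power is still above 99.9%.

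**3. Effect of adjustment.** The width is multiplied by √(1 − R²): 0.949, 0.894, 0.837 and 0.775 for R² = 0.1, 0.2, 0.3 and 0.4, a narrowing of 5%, 11%, 16% and 23%. At SD 1 and R² = 0.3 the half-width falls from 0.226 to 0.189 week. In a simulation with centre explaining 10% of the variance and a covariate 30% (both assumed), mean full width was 0.451 week unadjusted, 0.431 with centre, and 0.353 with both.

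**4. When this would matter.** Unadjusted power stays at or above 90% while SD ≤ √(n/2)/(1.96 + 1.282):

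- 150 per arm: 8.660/3.242 = 2.67 weeks
- 75 per arm: 6.124/3.242 = 1.89 weeks

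**5. Could the recorded SD be that large?** Take true healing times with the plan's mean 6 and SD 1. Assume each is dated to the first scheduled visit at which union is seen (the plan does not state a dating rule). The recorded values are then 4 weeks (2.3%), 6 weeks (47.7%) and 12 weeks (50%).

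- Mean = 0.0227×4 + 0.4772×6 + 0.5×12 = 8.95
- Variance = (0.0227×16 + 0.4772×36 + 0.5×144) − 8.954² = 89.54 − 80.18 = 9.36, so SD = 3.06 weeks

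With visit dates jittered by 0.5–1 week the simulated SD is 3.01–3.05. With a true mean of 5, 5.5, 6.5 or 7 weeks it is 2.2–2.9.

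**6. Power on that recorded scale, no true difference.** At 150 per arm, SE = 3.06 × 0.1155 = 0.353 and power = Φ(1/0.353 − 1.96) = Φ(0.87) = 81%. Simulation (4,000 runs per setting):

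| Per arm | Unadjusted | Adjusted, R² = 0.1 to 0.4 of true variance |
|---|---|---|
| 150 | about 81% | 84%, 85%, 88%, 91% |
| 75 | about 50% | 53% to 64% |

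Coarse dating also weakens the covariates. A near-even split into two values keeps about 2/π = 0.637 of the explained variance, so R² of 0.1–0.4 becomes 0.064–0.255 and the interval narrows by 3–14%, not 5–23%. Power is then Φ(2.83/√0.936 − 1.96) = 83% to Φ(2.83/√0.745 − 1.96) = 91%, in line with the simulation.

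If the recorded SD were 2.9 or 2.2 weeks, unadjusted power at 150 per arm would be Φ(1/(2.9×0.1155) − 1.96) = 85% or Φ(1/(2.2×0.1155) − 1.96) = 98%.

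**The case against.** The strongest reply is that nothing is broken. Under 1:1 randomisation the unadjusted intent-to-treat difference is unbiased, and its interval already allows for chance imbalance. With R² = 0.3 and SD 1, the covariate-driven part of the difference has SE √0.3 × √(2/150) = 0.063 week, a 95% range of about ±0.12 week against a 1-week margin. The plan has about seven times the patients it needs for this endpoint (150/21). All of this stands.

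A reader might infer three stronger claims, and the documents support none of them.

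- **That age and bone are strongly related to healing time.** The documents give no effect size or correlation for either within ages 3 to 14.
- **That the SD of 1 week leaves out the mix of ages and bones.** The sample-size text does not restrict the figure to one age or bone, so it can be read as a total SD.
- **That the healing comparison is invalid or underpowered as planned.** On the plan's own inputs it is neither.

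On crossover, the plan expects almost none. The pilot had one switch among 13 randomised children (one of the seven assigned to the operating room), with no sign that age or bone drove it. If switching is the worry, the choice of as-treated as primary is the larger issue. Adjustment helps only with confounding by the factors in the model.

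The remedy also needs detail: bone categories are undefined, and several sites expect only about 2 patients a year.

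**Conclusion.** The point holds as a minor, optional improvement, with moderate confidence. The comparison is unadjusted, and both the covariates and the stratification factor are at hand. The gain is a 5–23% narrower interval if R² is 0.1–0.4, which is an assumption, plus some protection against confounding by age and bone in the as-treated set.

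At SD 1 week the conclusion would not change at 150 or at 75 per arm. The gain becomes useful only if the recorded SD approaches or exceeds about 2.7 weeks (150 per arm) or 1.9 weeks (75 per arm). Visit-based dating could bring that about: at about 3 weeks, power rises from about 81% to about 84–91%. That scenario assumes union is dated to the first visit showing it, with true times centred near 6 weeks. It is weaker if the true mean lies away from 6 weeks.

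**What to change.** Before outcomes are compared by arm, pre-specify a linear model for healing time with these terms:

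- arm;
- centre, with small centres pooled by a stated rule or centre as a random effect;
- age, continuous;
- bone fractured, in categories fixed in advance with rare bones pooled.

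Judge non-inferiority on the adjusted ED minus OR difference and its two-sided 95% interval against 1 week, in both the as-treated and the intent-to-treat sets. Report the raw difference as a sensitivity analysis. State how union is dated between visits and how children without documented union are handled, since the model needs both.

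The cost is a short addition to the analysis text and the pooling rules. No new data, visits or patients are needed. Adjustment recovers part of the precision lost to coarse visit dating but does not cure it.
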